1.3.2 Secondary objectives

Secondary objectives of this study are:

- to evaluate the diagnostic parameters of diagnostic ultrasound that can be utilised to assess disease within the prostate gland.
- To evaluate the diagnostic parameters of diagnostic ultrasound that can be utilised to assess disease progression within the prostate gland.
- To evaluate if the intra and inter operator variability in the assessment of ultrasound imaging parameters of the prostate gland can be investigated.
- To determine if a suitable standardise imaging protocol and reporting tool or model could be utilised in the reporting of transrectal ultrasound imaging of the prostate.
- To gain a better understanding of how new ultrasound technology and techniques can be implemented and embedded into clinical practice.

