1.4 Study phases

This study is being undertaken as a PhD research project but within the NHS care setting. The study will consist of four phases:

1.4.1 Phase 1:

In this initial phase, eligible men who have consented to participate will undergo a transrectal ultrasound examination with a standard ultrasound probe and, at the same attendance a transrectal ultrasound examination with a new and novel probe using 29MHz scanning frequency. The images obtained from this examination will be retrospectively compared with the MRI imaging that has been obtained as part of the standard care pathway. The images obtained will be reviewed by two

health care practitioners with experience in prostate imaging and the outcomes of these reviews compared to evaluate agreement levels.

1.4.2 Phase 2:

The second phase of the study will evaluate the use of multiparametric standard and micro ultrasound in the assessment of men who are on an AS or WW pathway. This phase the study will evaluate if there are any changes in the findings at repeat ultrasound examinations that can indicate disease progression. Eligible men, who have consented to participate, will again undergo a transrectal ultrasound examination with a standard ultrasound probe and, at the same attendance a transrectal ultrasound examination with a new and novel probe using 29MHz scanning frequency.

1.4.3 Phase 3:

The process and acceptability of implementing new interventions and technologies into everyday clinical practice is frequently overlooked following research trials. This third phase will explore the views of the health care practitioners, who have consented to participate, regarding the use and implementation of the proposed new technologies; skill mix between these professional groups will be required for successful long term practice. The participants will be recruited from differing professionals within the staff groups of Hull University Teaching Hospitals NHS Trust. An adapted survey tool, derived from normalisation process theory framework, will be used to better understand how and if the new, complex, multi-parametric ultrasound techniques can be implemented within the organisational setting of everyday routine practice. A baseline assessment of confidence in knowledge and skills related to prostate cancer evaluation using ultrasound will be made.

1.4.3.1 Staff training:

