1.5.14 Data analysis

Once the database is complete for each participant, the lead researcher will compare the:

- ultrasound scores
- ultrasound colour Doppler findings
- prostate volume size
- lesion size

The above criteria will be compared between both the standard and micro-US imaging, and then the standard and micro-US with both MRI and histology. An assessment of agreement will be undertaken to evaluate the concordance between the two reviewers of the same images (Ranganathan, Pramesh and Aggarwal 2017). The relationship between these pairs will be evaluated using Bland-Altman plots. Scores from the ultrasound reviews will also be evaluated to determine inter-and intra-operator agreement between the randomly allocated reviewers. The inter-rater reliability, both within and across subgroups of reviewers, will be assessed using the intra-class correlation coefficient or the Cohen weighted kappa test (de Raadt et al. 2021).

1.6 Study design and methodology – Phase 2

Men eligible for AS will be invited to participate in phase 2. A multi-parametric US examination will be undertaken as part of the AS monitoring regime. Men under AS have a prostate serum antigen (PSA) blood test and digital rectal examination every 6 months. A multi-parametric US examination will be undertaken at these appointments to minimise unnecessary health care interactions for the participants. The multi-parametric US examination will be performed blinded to the previous examinations and histology results. The images will be scored and then correlated with previous imaging scores and current PSA levels. Any changes will be indicated to the lead urologist and the patients will be offered MRI imaging to evaluate any changes using existing gold standard imaging.

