1.6.6 Participation and patient contact

Following consultation and treatment choice the eligible patients will be given an information leaflet about the study. The lead researcher will be informed of the patients who have been approached by the specialist nurse. The lead researcher will then contact the patient by telephone and invite them to participate in the study. The phase 2 recruitment pathway is provided in [appendix 3](#). Once verbal consent has been given, a mutually convenient appointment will be made and confirmed with an appointment letter.

The patient will attend for agreed appointment and a face to face consultation with the lead researcher will be undertaken to discuss the study and obtain written consent. The lead researcher will be blinded to the results of the MRI and any previous ultrasound image collection at this time to minimise undue coercion into the study, as in phase 1.

1.6.7 Image collection Phase 2

The [ultrasound examination](#) described and image collection for phase 2 is identical to that of [phase 1](#). The exception being that once the images have been collected and stored the patient will be free to leave; no further consultation, procedure or examination will be undertaken.

1.6.8 Data collection phase 2

The data collection of phase 2 is identical to that of [phase 1](#). Data collections forms utilised are attached in [Appendix 6](#) & [Appendix 7](#). The current standard and micro-ultrasound collected as part of phase 2 will be reviewed by two randomly allocated reviewers and scored as outlined above.

1.6.9 Data assessment phase 2

Once scored the documented criteria will be compared between both the standard and micro-US imaging collected during phase 2, and then compared with the previous standard and micro-US imaging [collected](#) during [phase 1](#).

1.6.10 Data analysis phase 2

The relationship between these pairs will be evaluated using Bland-Altman plots as per [phase 1](#). Scores from the ultrasound reviews will also be evaluated to determine inter-and intra-operator agreement between the randomly allocated reviewers. The phase 1 images and cine loop are the baseline data that all subsequent phase 2 examinations undertaken on that particular participant will be compared.

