Any changes between the initial ultrasound scores and subsequent scores obtained during the longitudinal phase 2 study will be alerted to the lead clinical supervisor (Consultant Urologist) and the patient will be reviewed at the next MDT.

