1.10.2.2 Burden

There is a greater burden to phase 2. This is an examination over and above standard care. The patient will need to tolerate a rectal ultrasound examination every 6 months. As this new technology is being investigated it is not a diagnostic examination and will not provide diagnostic or prognostic results for the individual participant. The burden of dealing with the unknown will be explained to the participant and access to urology specialists will be available at all times. Should any findings of concern be detected on evaluation of the multi-parametric US these will be alerted to the lead urologist and arrangements for MRI will be made. Any changes on MRI compared to the baseline imaging will necessitate diagnostic biopsy.

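### The visible phase 2 analysis text does not set an ultrasound change against the MRI, or clearly against the biopsy, that the change triggers

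*Protocol*

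**What the plan says.** **The question.** Protocol 1.4.2 says phase 2 will "evaluate if there are any changes in the findings at repeat ultrasound examinations that can indicate disease progression". One of the secondary objectives in 1.3.2 is "To evaluate the diagnostic parameters of diagnostic ultrasound that can be utilised to assess disease progression within the prostate gland".

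**The phase 2 comparisons.** Under 1.6.9 the scored criteria are "compared between both the standard and micro-US imaging collected during phase 2, and then compared with the previous standard and micro-US imaging" from phase 1. Section 1.6.10 applies Bland-Altman plots to these pairs and adds inter- and intra-operator agreement. The opening of 1.6 adds: "The images will be scored and then correlated with previous imaging scores and current PSA levels".

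**What follows a change.** Section 1.6.10 says "Any changes between the initial ultrasound scores and subsequent scores obtained during the longitudinal phase 2 study will be alerted" to the consultant urologist, with review at the next MDT. Section 1.6 says "the patients will be offered MRI imaging to evaluate any changes using existing gold standard imaging". Section 1.10.2.2 continues: "Any changes on MRI compared to the baseline imaging will necessitate diagnostic biopsy".

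**Phase 1 for contrast.** Section 1.5.14 compares the two probes with each other, "and then the standard and micro-US with both MRI and histology".

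**The concern.** The pathway in 1.6 and 1.10.2.2 produces a check on the phase 2 question. A man whose ultrasound changes is offered the test that the protocol itself calls the gold standard, and a changed MRI leads to tissue. The comparisons in 1.6, 1.6.9 and 1.6.10 do not take up those results.

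A change in ultrasound score can come from the disease, from the reader or from the acquisition of the scan. Probe-to-probe comparison, reader agreement and comparison with the baseline scan describe the size and repeatability of a change. They do not show whether it was progression. Current PSA is the only contemporaneous non-ultrasound measure named, and the protocol does not call it a gold standard. Phase 2 could therefore close with a description of score changes and their correlation with PSA, and without the number of alerted men in whom MRI or histology confirmed progression.

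**Working it through.** The protocol states no power, effect size or alert rate for phase 2, so there is no figure to reproduce. The check is a comparison of the text, followed by an illustration of precision.

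**1. Comparators, phase by phase**

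| Item | Phase 1 | Phase 2 |
|---|---|---|
| Other probe | 1.5.14 | 1.6.9 |
| Earlier imaging | not applicable | 1.6, 1.6.9 |
| Readers | 1.5.14 | 1.6.10 |
| Current PSA | recorded (1.5.13) | correlated (1.6) |
| MRI | compared (1.5.14) | offered after a change (1.6); not named as a comparator in 1.6.9 or 1.6.10 |
| Histology | compared (1.5.14) | follows a changed MRI (1.10.2.2); not named as a comparator in 1.6.9 or 1.6.10 |

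The benefit section for phase 2 (1.10.2.3) says the images can be correlated with previous MRI and with histology when there is any. The MRI there is the earlier one, not the triggered one. The histology could include a triggered biopsy. It is a statement of benefit and not part of the analysis text.

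**2. What the triggered results can estimate**

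The trigger works in steps: ultrasound change, then MRI offer, then biopsy if the MRI has changed. Among alerted men this gives

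confirmed share = men with progression confirmed / men alerted,

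with men whose MRI or biopsy was not done shown as not verified.

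It does not give sensitivity. If only alerted men are verified, no missed case can be observed, so the apparent value is TP / (TP + 0) = 1.0 whatever the true value is.

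**3. Precision**

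Inputs: maximum of 30 men (1.6.2). The alert numbers and confirmed shares are assumptions.

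Exact (Clopper-Pearson) 95% interval for x confirmed of n alerted:
- lower limit = the 0.025 quantile of Beta(x, n − x + 1)
- upper limit = the 0.975 quantile of Beta(x + 1, n − x)

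| Assumed alerted, n | Assumed confirmed, x | Exact 95% interval |
|---|---|---|
| 3 (10% of 30) | 1 | 1% to 91% |
| 6 (20% of 30) | 3 | 12% to 88% |
| 9 (30% of 30) | 4 | 14% to 79% |
| 10 | 5 | 19% to 81% |
| 20 | 10 | 27% to 73% |
| 30 (every man) | 15 | 31% to 69% |

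Shares near one half give about the widest interval for each n. Even with every man alerted, the interval spans 69 − 31 = 38 percentage points.

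**The case against.** **The design section already gives MRI this role.** The MRI offer in 1.6 stands under phase 2 methodology, directly after the correlation sentence, and its stated purpose is to evaluate the change. Section 1.10.2.3 adds that ultrasound is unlikely to be diagnostic before it has been compared with the gold standards. This shows intent, and it stands to that extent. But the second remark also appears for phase 1 (1.10.1.3), so it does not settle what phase 2 will analyse, and 1.6.10 stops at alert and MDT review.

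**Recording.** A reader might infer that the triggered results would not be recorded, because phase 2 has no collation section of its own. The protocol does not support that. Phase 2 scores are to be correlated with current PSA, and PSA enters the database only under 1.5.13, which suggests that collation carries over. Section 1.5.13 also covers the histology of any biopsy performed. Its MRI sentence is tied to the standard care pathway, so follow-up MRI is less clear, and a confirming sentence is enough.

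**Biopsy.** A reader might also infer that histology is absent from phase 2. That goes too far, because the mention in 1.10.2.3 can be read to include a triggered biopsy. It is fair to say only that the biopsy is not clearly named as the reference.

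**Unseen material.** Appendix 5 (phase 2 image review pathway) and Appendix 3 (phase 2 recruitment) could not be read, and an SAP may exist. Either appendix might show the comparison. The layout of a table belongs in an SAP. The reference for a phase 2 change is a different matter, because the protocol itself lists comparators for both phases.

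**Too few men.** The intervals are indeed wide, which argues for a descriptive report and not for leaving the results out.

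**Conclusion.** The point holds in a limited form. The visible text of 1.6, 1.6.9 and 1.6.10 compares repeat ultrasound with the other probe, earlier imaging, readers and current PSA. It does not name the triggered MRI, or clearly name the biopsy after it, as the reference for whether an ultrasound change indicates progression. Phase 1 does use MRI and histology.

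The size cannot be put as a number of men, since no alert rate is given and 30 is only the ceiling. What is at stake is whether phase 2 can speak to its own question among alerted men.

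A reader might infer that adding these results would show how much progression ultrasound misses, or answer the Summary's question whether MRIs can safely be reduced. It would do neither, because men without an alert have no triggered reference test.

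The conclusion rests on the readable text. If Appendix 5 already shows the comparison, all that remains is to state it in 1.6.10. This is a cheap improvement, not a flaw that invalidates the phase.

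**What to change.** Add to 1.6.10, in substance:

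- Ultrasound changes in phase 2 will be compared with the result of the MRI they trigger and of any biopsy that follows.
- The number and share of alerted men with progression confirmed, not confirmed, or not verified (MRI or biopsy not done) will be reported descriptively with exact 95% intervals.
- Men without an alert have no triggered reference test, so neither missed progression nor a safe reduction in MRIs can be estimated from these results.

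Confirm in 1.6.8 or 1.6.10 that the recording of PI-RADS and histology in 1.5.13 applies to phase 2 follow-up tests. The table layout can be left to the SAP.

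The cost is protocol wording and a short descriptive table built from results that the clinical pathway already produces. It needs no extra scans or patients, and the pathway is unchanged. The drawback is wide intervals, which should be reported as such.

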1.5.1 Phase 1: Patient population

With consent, all eligible men will be invited to participate in the first phase of the study; [appendix 1](#) outlines the current care pathway and the eligibility criteria utilised in this study. Multi-parametric US will be used to assess the prostate gland prior to the ultrasound guided diagnostic prostate biopsies which is performed as part of routine care. The multi-parametric US examination will be performed blinded to the pre-biopsy MRI undertaken as part of routine care. Multi-parametric US findings will be scored and subsequently correlated to MRI and any related histology findings which are recorded as part of routine care.

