1.5.7 Phase 1 recruitment process

Patients are seen in a specific prostate assessment clinic by a urology nurse specialist. A clinical history is taken and from there, referrals for both MRI and ultrasound guided prostate biopsy are made. At this appointment, all patients will be given an information leaflet for the study. The MRI is undertaken within 14 days of referral; the ultrasound guided prostate biopsy can only be performed following the MRI. The MRI can be distorted due to post biopsy haemorrhage in the prostate gland, and, more importantly, the MRI provides crucial information related to suspected areas of pathology in the gland which are targeted during the biopsy procedure. During the time from referral to MRI the patient will be contacted by the lead researcher and invited into the ultrasound study.

1.5.8 Ultrasound appointments – phase 1

A mutually convenient appointment will be made and confirmed with an appointment letter. The phase 1 recruitment pathway is provided in [appendix 2](#). The patient will attend at the agreed date and time and a face to face consultation with the lead researcher will be undertaken to discuss the study and obtain written consent. The lead researcher will be blinded to the results of the MRI or previous studies at this time to minimise undue coercion into the study.

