1.10.1.1 Risk

There is minimal risk to patients participating in phase 1 of the study. A trans-rectal ultrasound examination of the prostate will be performed prior to any standard care being undertaken. The standard care for patients with MRI PI-RADS score 3, 4 or 5 is to have a transrectal ultrasound probe inserted into the rectum, the prostate identified and appropriate biopsy sites determined. The majority of men tolerate this procedure well. The multi-parametric US examination will involve a probe being inserted into the rectum, images taken and stored for evaluation later. The probe will then be withdrawn and standard care will commence.

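### The phase 2 baseline is a pre-biopsy scan, so in biopsied men change from baseline may include a biopsy effect that the planned comparison cannot separate from disease change

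*Protocol*

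**What the plan says.** Order of scan and biopsy. Section 1.5.1: "Multi-parametric US will be used to assess the prostate gland prior to the ultrasound guided diagnostic prostate biopsies". Section 1.10.1.1 confirms the order within the attendance: "The probe will then be withdrawn and standard care will commence". For men with PI-RADS 3 to 5, that care is the biopsy.

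Baseline. Section 1.6.10: "The phase 1 images and cine loop are the baseline data that all subsequent phase 2 examinations" of that participant are compared with. Section 1.6.9 names the phase 1 imaging as the earlier comparator. Section 1.6 speaks more loosely of correlating phase 2 scores with previous imaging scores.

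Use of a change. Section 1.6.10: "Any changes between the initial ultrasound scores and subsequent scores obtained during the longitudinal phase 2 study will be alerted" to the supervising urologist, with review at the MDT. Section 1.6 adds an offer of MRI.

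Biopsy effect on imaging. Section 1.5.7: "The MRI can be distorted due to post biopsy haemorrhage in the prostate gland". Nothing comparable is said about ultrasound.

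Timing of phase 2 scans. Section 1.6: "Men under AS have a prostate serum antigen (PSA) blood test and digital rectal examination every 6 months", and "A multi-parametric US examination will be undertaken at these appointments to minimise unnecessary health care interactions for the participants". Section 1.6.6 says that, after the treatment choice and verbal consent, "a mutually convenient appointment will be made and confirmed with an appointment letter".

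Who enters. Section 1.6.3 requires known cancer of Gleason 6 or less. Section 1.6.1 also invites men with PI-RADS 1 or 2, who under section 1.5.2 are not biopsied.

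**The concern.** Phase 2 exists to find ultrasound changes that point to progression; this is the second of the secondary objectives in section 1.3.2. A man on active surveillance with a Gleason grade has normally been biopsied. If he was scanned in phase 1, his baseline is pre-biopsy and all his follow-up is post-biopsy. Time and biopsy then move together in the planned comparison.

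The scored features are echo pattern, focal areas and Doppler signal (section 1.5.12). If a biopsy leaves a trace in any of them, a parameter could look like a marker of progression when it marks the biopsy, and the alert would be raised for the same reason. The protocol takes the possibility seriously for MRI but does not carry the question over to ultrasound.

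**Working it through.** **1. Structure.** No figure in the protocol is at issue, so the passages are set side by side.

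- Phase 1 scan before biopsy: sections 1.5.1 and 1.10.1.1.
- Phase 1 scan is the baseline for all phase 2 scans of that man: section 1.6.10.
- It follows that, in a man with a phase 1 scan and a later biopsy, each change from baseline has the biopsy in between.
- No post-biopsy reference scan and no interval from biopsy to first phase 2 scan is stated in the text.

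**2. How many men could give a post-biopsy pair.** Inputs: recruitment up to 18 months (1.6.2), imaging over 24 months (summary), scans every 6 months (1.6, 1.6.3). Assumption: entry month t is spread evenly over 0 to 18. Follow-up scans = floor((24 − t − L)/6), where L is the delay in months from the phase 1 scan to the start of the 6-monthly clock.

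| L (assumed) | no scan | one | two | three | two or more |
|---|---|---|---|---|---|
| 0 | 0% | 33% | 33% | 33% | 67% |
| 1 | 6% | 33% | 33% | 28% | 61% |
| 3 | 17% | 33% | 33% | 17% | 50% |

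On these assumptions between a half and two thirds of the men would have two post-biopsy scans, that is 15 to 20 if the maximum of 30 is reached and all were biopsied. A third would have exactly one.

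**3. What a biopsy effect would do, if there is one.** Let d be the chance of progression and b the chance of a biopsy-related score change. Neither is in the document, so both are assumed. They are taken as independent, and every progression is taken to change the score.

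- P(score change) = 1 − (1 − d)(1 − b)
- Share of changes without progression = (1 − d)b / P(score change)

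For 30 biopsied men and d = 10%:

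- b = 0: 30 × 0.10 = 3.0 change, 0% of them without progression.
- b = 10%: 30 × (1 − 0.90 × 0.90) = 5.7 change; 0.09/0.19 = 47% without progression.
- b = 30%: 30 × (1 − 0.90 × 0.70) = 11.1 change; 0.27/0.37 = 73% without progression.

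Over d = 5% to 20% and b = 0 to 30% the share runs from 0 to 85% (upper end: d = 5%, b = 30%, 0.285/0.335). The result depends chiefly on b, and b = 0 is compatible with everything the document says.

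**The case against.** The strongest reply is that no biopsy effect on ultrasound is shown. Section 1.5.7 concerns MRI, says only that distortion can occur, and gives no duration. Sections 1.6, 1.6.3 and 1.10.2.2 all point to 6-monthly scans, by which time an effect may have gone. This stands, and it limits the point to a possible effect.

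The appointment wording in section 1.6.6 repeats that of section 1.5.8 and need not mean an early scan. That is fair, and the flow chart in Appendix 3, which was not available, may give the timing. Still, the text does not say when the first phase 2 scan falls.

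Partial safeguards exist. Section 1.6 mentions previous imaging scores, and a flagged man is offered MRI, so a score change is not taken as progression. But sections 1.6.9 and 1.6.10 name only phase 1 as the comparator. The MRI is read against baseline imaging (1.10.2.2), and the diagnostic MRI is also pre-biopsy.

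It could also be said that separate display of biopsied and unbiopsied men belongs in an analysis plan. That may be so, but the baseline is fixed in the protocol itself.

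A reader might go further and infer that every biopsied man carries a biopsy effect, that the error always runs towards apparent change, or that spurious changes outnumber true ones. The document supports none of these. On the last, assume spurious change in 5% to 20% of 30 men: 1.5 to 6 men. Even entry over 18 months gives a mean follow-up of 24 − 9 = 15 months, hence 30 × 1.25 = 37.5 person-years. At an assumed 3% to 10% per year this is 1.1 to 3.75 progressions. The ranges overlap, so no order follows.

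A reader might also want the first phase 2 scan to replace phase 1 as the baseline. That is a trade-off: an early scan could itself carry biopsy artefact, and men with a single follow-up scan would lose their only comparison.

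**Conclusion.** The point holds as a limit of the design. In men biopsied after a phase 1 scan, the planned change from baseline spans the biopsy and cannot separate a biopsy effect from disease change. This rests on the text alone. It does not reach men who enter phase 2 without a phase 1 scan, which section 1.6.5 appears to allow, or unbiopsied men.

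The size is unknown. The range of 0 to 85% in the working comes from assumed rates and includes zero. This is a cheap improvement of low priority, not a fault that undermines phase 2.

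**What to change.** Leave the phase 1 baseline and the alert rule in section 1.6.10 as they are. Add to sections 1.6.9 and 1.6.10:

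- (a) For men with two or more phase 2 scans, change between post-biopsy phase 2 scans is also reported, and is used alongside change from phase 1 when judging which parameters indicate progression.
- (b) The biopsy date and the days from biopsy to each scan are recorded, and change from phase 1 to the first phase 2 scan is labelled as spanning the biopsy.
- (c) Biopsied and unbiopsied men are shown separately, so far as unbiopsied men enter; sections 1.6.1 and 1.6.3 disagree on that.

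Sections 1.6 and 1.6.6 should state consistently when the first phase 2 scan takes place; which timing is for the investigators to decide.

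Cost: one date field and a little more analysis, with no extra scan. Men with only one phase 2 scan, about a third under the even-entry assumption, still contribute only the comparison across the biopsy.
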